11.6.2. NYHA Class

NYHA Class assessment shall be performed by a site staff who is blinded to the study design, subject's clinical status in the study, and the programmed device settings. The subject's current NYHA Class must be determined based on **Table 11.4-1**.

11.6.3. Patient Global Assessment

The current PGA must be filled out by the subject, as specified in the assessment tool in **Table 11.5-1**.

11.6.4. Physician Global Assessment

The current Physician Global Assessment (PhGA) will be filled out by the investigator/delegated site staff based on the evaluation of the subject's status from multiple clinical aspects. A comparison of the assessment tool for the PGA and PhGA is shown in **Table 11.5-1**.

11.6.5. Response Status Determination

Based on the subject's vital status, NYHA class, PGA, and occurrence of HF event, the investigator/delegated site staff will classify each subject in the Non-Responder Group to be either a responder or a non-responder per the following criteria:

- Responder: subjects with an Improved CCS score
- Non-Responder: subjects with a Worsened or unchanged CCS score

The PhGA will not be used in classifying the subject response status. All subjects in the Non-Responder Group will complete the study at the end of their 12 Month Visit.

All reported hospitalization and events that meet the definition of HF event will be adjudicated by the Clinical Events Committee (CEC) for relatedness to the heart failure.

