11.6.1.1. HF Event Definition

For the purpose of the CCS calculation, HF event is defined as an adverse event with a primary cause of HF and either of the conditions below is met:

- Subject is admitted and discharged with a calendar date change.
- Subject is not hospitalized but received one or more IV medications including diuretics, inotropes, vasodilators, other parenteral therapy, or aquapheresis.

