11.6.17. Adverse Event Assessment

Study required adverse event data will be collected and assessed for each subject. Hospitalization records are required to be sent to BSC. See **Section 20** for Adverse Event collection and reporting requirements.

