11.6.18. HeartLogic Alert

The HeartLogic Alert feature is newly available in the Resonate family of devices. If the HeartLogic Alert feature is turned on, then the HeartLogic Alert(s) that resulted in a change in the subject's medical treatment will be collected.

11.6.19. "Save All" Device Data

Device data is required to be downloaded on a USB disk using "Save All" method if the subject is not enrolled in the LATITUDE Remote Monitoring System. Downloading the data requires ending the PRM session with the device. Hence, it is recommended to complete all other study activities that require PRM-device communication prior to this step. For subjects enrolled in the LATITUDE Remote Monitoring System, device data will be transmitted to BSC automatically on a regular basis and do not require manual download.

The original USB disk will be retained at the site and a copy of the disk should be submitted to BSC quarterly or more frequently. Label the Subject ID and visit information (6 Month or 12 Month) on both USB disks. The data collected in this section will be used for future product feature enhancement or development, and are not associated with the primary and ancillary objectives. A deviation is not required if the "Save All" USB disk is not performed or submitted to BSC.

A summary of the source documentation required at the 12 Month Visit is described in **Table 11.6-1**.

Table 11.6-1: Source Documentation Requirement at the 12 Month Visit

Source Documentation Requirement	Disposition
NYHA class assessment	Retain at study site
Patient Global Assessment	
Physician Global Assessment	
Adverse event assessment	
Device Settings Report, Settings Changes Report, Quick Notes Report, LV VectorGuide Report	
Hospitalization record	
Echo measurement, if performed per standard of care	
Manually recorded Charge Remaining	
ECG/EGM Strips from the SmartDelay test	Retain at study site Submit 1 copy to BSC
ECG/EGM Strips from the RVp-LVs interval test	
“Save All” device data USB disk, if applicable	

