20.1. Reportable Events by Investigational Site to BSC

The communication requirements for reporting adverse events, device deficiencies, failures, malfunctions, and product nonconformities to BSC are listed in **Table 20.4-1**. Adverse events must always be reported through the eDC system for SMART MSP Study. However, in cases where the eDC is not available, report the adverse event to BSC using [contact]. It is the responsibility of the investigator to assess and report all reportable events in the following categories:

- All Serious Adverse Events
- All Heart Failure and Cardiac related Adverse Events requiring IV or invasive therapy, including new onset of cardiac events, or worsening in severity or frequency of pre-existing condition(s)
- All Adverse Device Effects
 - Events listed in the arrhythmia logbook should be reported only if determined to be clinically significant by the investigator and/or delegated site staff (such events include ATR, PMT, etc.)

- All arrhythmias which received inappropriate therapy (i.e. inappropriate shock) must be reported
- Include adverse events related to any part of the implanted CRT-D system
- All Device Deficiencies
- All Adverse Events related to the protocol required testing, excluding PNS during lead testing.
- Unanticipated Adverse Device Effects/Unanticipated Serious Adverse Device Effects

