20.8. Source Documents for CEC Adjudication

All post-enrollment hospitalizations except the hospitalization in which the existing device implant is performed will be adjudicated by the CEC per **Section 22.2**. Source documents required for adjudication include, but are not limited to: admission note, history and physical, consultation notes, medication lists and discharge summary.

21. Informed Consent

Subject participation in this clinical study is voluntary. Informed Consent is required from each subject. The Investigator is responsible for ensuring that Informed Consent is obtained prior to the study-required procedures and/or testing and data collection.

The obtaining and documentation of Informed Consent must be in accordance with the principles of the Declaration of Helsinki, any applicable national regulations, and local IRB and/or Regulatory authority body, as applicable. The ICF must be accepted by BSC or its delegate (e.g. CRO), and approved by the site's IRB, or central IRB, if applicable.

Boston Scientific will provide a study-specific template of the ICF to investigators participating in this study. The ICF template may be modified to meet the requirements of the investigative site's IRB. Any modification requires acceptance from BSC prior to use of the form. The ICF must be in a language understandable to the subject and if needed, BSC will assist the site in obtaining a written consent translation. Translated consent forms must also have IRB approval prior to their use. Privacy language shall be included in the body of the form or as a separate form as applicable.

The process of obtaining Informed Consent shall at a minimum include the following steps, as well as any other steps required by applicable laws, rules, regulations and guidelines:

- be conducted by the Principal Investigator or designee authorized to conduct the process,
- include a description of all aspects of the clinical study that are relevant to the subject's decision to participate throughout the clinical study,
- avoid any coercion of or undue influence of subjects to participate,
- not waive or appear to waive subject's legal rights,
- use native language that is non-technical and understandable to the subject,
- provide ample time for the subject to consider participation and ask questions if necessary,
- ensure important new information is provided to new and existing subjects throughout the clinical study.

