A Clinical Events Committee (CEC) is an independent group of individuals with pertinent expertise that reviews and adjudicates the following events, as a component used in determining the Primary Effectiveness Endpoint, as reported by study investigators:

- All hospitalizations
- Any event where a study subject is not hospitalized but received one or more IV medications including diuretics, inotropes, vasodilators, other parenteral therapy, or aquapheresis.
- Other events at the discretion of BSC

The CEC will review a safety event dossier, which may include copies of subject source documents provided by the study sites, for all applicable events. Investigative sites are requested to send source documents related to the event to [contact].

Committee members will include a minimum of three practitioners with training in Electrophysiology (EP), and/ or Cardiology with the necessary therapeutic and subject matter expertise to adjudicate heart failure event. CEC responsibilities, qualifications, membership, and committee procedures are outlined in the CEC charter.

23. Suspension or Termination

23.1. *Premature Termination of the Study*

Boston Scientific Corporation reserves the right to terminate the study at any stage but intends to exercise this right only for valid scientific or administrative reasons and reasons related to protection of subjects. Investigators, associated IRBs/ECs, and regulatory authorities, as applicable, will be notified in writing in the event of study termination.

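### Sections 11.5.5 and 11.6.5 let the site judge the cause of an outpatient IV-therapy event before the CEC sees it, unlike 22.2, and 20.1 leaves some such events unreported; the likely effect on the primary endpoint is small

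*Combined protocol and SAP*

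**What the plan says.** Five places bear on which events the CEC judges.

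- **11.6.5 (12 Month Visit):** "All reported hospitalization and events that meet the definition of HF event will be adjudicated by the Clinical Events Committee (CEC", the question for the committee being relatedness to heart failure. Section 11.5.5 uses almost the same wording at 6 months. Section 12.4.3 speaks of adjudicating the reported HF event and gives control of variability between sites as the reason.
- **11.6.1.1 (definition):** "HF event is defined as an adverse event with a primary cause of HF and either of the conditions below is met". One condition is an admission with a change of calendar date. The other is "Subject is not hospitalized but received one or more IV medications including diuretics, inotropes, vasodilators, other parenteral therapy, or aquapheresis".
- **22.2 (CEC remit):** all hospitalizations, and "Any event where a study subject is not hospitalized but received one or more IV medications including diuretics" or the other listed therapies. There is no condition on cause, but the remit is limited to events that investigators report.
- **20.1 (what sites must report):** among other categories, "All Heart Failure and Cardiac related Adverse Events requiring IV or invasive therapy".
- **20.8 (source documents):** "All post-enrollment hospitalizations except the hospitalization in which the existing device implant is performed will be adjudicated by the CEC". Outpatient IV events are not named.

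Under 11.6.5 the investigator or delegated site staff classify each subject as responder or non-responder. Section 11.6.2 requires blinding of the NYHA assessor. No such requirement is stated for the staff who classify response or report events.

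**The concern.** Whether an outpatient course of IV therapy was given for heart failure is the question the CEC is there to answer. If the event goes to the CEC only once it meets a definition that includes HF as primary cause, that question has been answered first at the site. A site that follows 11.6.5 literally would withhold an event that 22.2 expects the committee to review.

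The reporting rule leaves a second, narrower gap. Take a non-serious outpatient course of IV diuretic for fluid overload that the site confidently attributes to renal disease. It fits no reportable category in 20.1, so it cannot reach the CEC under 22.2 either.

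The stake is the 12-month endpoint. Under 11.6.1.4 an HF event makes a subject Worsened. Without it, a subject who is better on NYHA class or Patient Global Assessment (PGA), and worse on neither, is Improved. In a single-arm study with no concurrent control, an error in that direction adds directly to the count tested against the 5% goal.

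**Working it through.** **Step 1: routes to the CEC, as written.**

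| Event | 11.5.5 / 11.6.5 | 20.1 report required? | 22.2 |
|---|---|---|---|
| Hospitalization, any cause | yes, if reported | yes, if it is an SAE | yes, if reported |
| Outpatient IV, site says HF | yes | yes | yes |
| Outpatient IV, site says cardiac but not HF | no | yes | yes |
| Outpatient IV, non-serious, site confidently says non-cardiac, not device- or testing-related | no | no | only if reported anyway |

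The third row is the direct conflict between 11.5.5/11.6.5 and 22.2. The fourth is the reporting gap.

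**Step 2: the plan's own design.** Inputs from 12.1.2.2: N = 110, goal 5%, expected rate 15%, one-sided 5%, exact binomial test, stated power 95%. The exact lower limit for x Improved is the 5th percentile of Beta(x, 110 − x + 1).

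- x = 9: lower limit 4.33%, fails.
- x = 10: lower limit 5.02%, passes.
- P(Bin(110, 0.05) ≥ 10) = 4.9%, and P(Bin(110, 0.15) ≥ 10) = 97.6%.

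The power is above the stated 95%. N = 110 with 95.2% power is what a one-sided 2.5% test with pass mark 11 gives. This is context only and does not affect the point.

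**Step 3: leverage of a wrongly Improved subject.** Suppose the true rate under full adjudication is 5% and k subjects are wrongly Improved. Then P(pass | k) = P(k + Bin(110 − k, 0.05) ≥ 10).

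| k | P(pass) |
|---|---|
| 0 | 4.9% |
| 1 | 9.6% |
| 2 | 17.3% |
| 3 | 28.8% |

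**Step 4: from exposed to wrongly Improved.** The documents give no rate of outpatient IV therapy. Assume 3% to 6% of 110 subjects have such an event (3.3 to 6.6 subjects) and that a quarter to a half of the events are HF events labelled non-HF. Then 3.3 × 0.25 = 0.8 and 6.6 × 0.5 = 3.3, or about m = 1 to 3 exposed subjects. An exposed subject changes the endpoint only if otherwise Improved. Assume probability q for that, from 5% to 25%, a range that contains the plan's 5% goal and 15% expected rate. With K ~ Bin(m, q), P(pass) = Σ P(K = k) × P(pass | k).

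- m = 1, q = 5%: 0.95 × 4.92% + 0.05 × 9.60% = 5.2%.
- m = 3, q = 15%: 7.2% (0.45 subjects wrongly Improved on average).
- m = 3, q = 25%: 0.422 × 4.92% + 0.422 × 9.60% + 0.141 × 17.33% + 0.016 × 28.79% = 9.0%.

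**The case against.** The strongest reply is that 11.6.5 need not be read as site screening. It sends events to the CEC to determine relatedness to heart failure, which would be pointless if the site had settled cause. If meeting the definition means only meeting its admission or IV-therapy limb, 11.6.5 agrees with 22.2. That reading is possible. But the definition puts primary cause in its main clause, and nothing tells a site to ignore it. The wording is at best ambiguous on the route into a primary endpoint.

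Several stronger readings are tempting, and the documents do not support them.

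- *Reporting is required only for events the site calls HF or cardiac.* Section 20.1 also covers all serious adverse events, adverse device effects and testing-related events, and asks for submission when the category is unclear. These routes also rest on site judgement, but the gap is confined to non-serious events confidently called non-cardiac.
- *Sections 20.1 and 22.2 contradict each other.* Section 22.2 covers events as reported by investigators, so 20.1 limits its reach without contradicting it.
- *The CEC gets no source documents for IV events.* Section 22.2 asks sites for documents on the events it covers; 20.8 merely fails to name outpatient IV events.
- *True non-responders are released at 6 months.* Section 11.5.5 keeps any subject with reported hospitalization or IV therapy in follow-up as a non-responder, whatever the score. Only an unreported event escapes, and a subject released that way never enters the LV MSP Group and cannot add to its Improved count.
- *Hospitalization records stay at the site because Table 11.6-1 lists them for retention there.* Section 11.6.17 says "Hospitalization records are required to be sent to BSC", and 11.5.17 and 11.7.1 say the same. The table is a clerical matter.

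**Conclusion.** The inconsistency is real. Sections 11.5.5 and 11.6.5, with the wording of 12.4.3, make CEC review of an outpatient IV event depend on the causal judgement the CEC should make; 22.2 does not. Section 20.1 adds a narrow reporting gap. At 12 months, site staff who are not described as blinded can therefore make the decisive call for these events.

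The size is small. The 9.6% and 17.3% figures are what one or two subjects actually misclassified as Improved would do; a reader might take them as the expected inflation, but an exposed subject need not be otherwise Improved. Under the assumptions above, the chance of passing at a true 5% rate moves from 4.9% to about 5.2% to 9.0%. That range rests on three assumed quantities: the event rate, the mislabelled share, and the chance that an exposed subject is otherwise Improved. The documents supply none of them. The point is worth correcting because the pass mark turns on one subject and the remedy is cheap. It does not show that the endpoint is materially biased.

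**What to change.** 1. In 11.5.5, 11.6.5 and 12.4.3, replace the condition that an event meet the HF-event definition with the pool in 22.2: all hospitalizations, and any non-hospitalized event treated with IV diuretics, inotropes, vasodilators, other parenteral therapy or aquapheresis, whatever cause the site assigns. The list should match 22.2 and 11.6.1.1 in full.
2. In 20.1, make those outpatient IV-therapy events reportable regardless of attributed cause.
3. In 20.8, name them beside hospitalizations, so that the source-document rule covers the same pool.

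The cost is protocol wording, some additional event reports from sites, and some more dossiers for a committee whose remit already covers reported events of this kind. No visit, test, sample size or analysis method changes.

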11.6.6. Echocardiography Measurement

If an echocardiography was performed by the standard of care since last visit, collect the subject's most recently obtained echo values and the date of measurement.

- LVEF
- LVESV
- LVEDV
- Aortic VTI

- Mitral Valve Regurgitation

11.6.7. Current Device Settings and Status

Print a copy of the Quick Notes Report from the PRM to document current device settings and status prior to conducting any test and changing the programming settings. A list of settings and status, including but not limited to the SmartDelay settings, percent of pacing (%RA paced, % RV paced, %LVa paced, and %LVb paced), and percent of AT/AF (%AT/AF) are required to be collected.

The investigator may have turned off the LV MSP feature if a subject experienced worsening symptoms prior to the 12 Month Visit. A rationale and study deviation are required if the LV MSP feature is turned off prior to the 12 Month Visit.

11.6.8. Lead Measurements

The following lead measurements are required to be collected for the RA lead, RV lead, and LV lead:

- Intrinsic amplitude (mV)
- Pacing capture threshold (PCT in V; the recommended pulse width is 0.4 ms)
- Pacing lead impedance (Ω)
- Shocking lead impedance (Ω , RV lead)

The following document is required for the RA lead, RV lead, and LV lead measurements:

- Print a copy of the Quick Notes Report from the PRM.

Lead measurement testing is required unless a rationale is provided. For example, the measurement is prohibited by a subject's condition.

It is recommended that the PCT measurements be collected in the following fashion:

- At least 3 cardiac cycles at a given voltage level are obtained before stepping down to the next voltage level.
- A count of two non-capture beats at a given voltage level is reached before declaring a loss of capture (LOC) for any of these tests.

It is recommended that the threshold be defined as one voltage level above the level where two non-captured beats are observed. If multiple PCT tests were performed, only the final measurement is required to be entered on the CRF.

11.6.9. SmartDelay Test

It is required to perform the SmartDelay test for all subjects to obtain programming recommendations for the AV Delay and Pacing Chamber. It is per the investigator discretion whether to follow the programming recommendations. The pacing chamber is selected for the subject at the Enrollment Visit. There is no requirement to keep the same pacing chamber

at the end of the 12 Month Visit as all subjects in the Non-Responder Group will complete the study at their 12 Month Visit.

The LV offset is required to be set at 0 ms prior to running the SmartDelay test.

The SmartDelay test nominal Temporary Paced Lower Rate Limit (LRL) is set at 80 bpm. It is recommended to set the LRL at 10 to 15 bpm above the subject's intrinsic heart rate before conducting the SmartDelay test.

The following values from the SmartDelay test are required to be collected:

- SAV and PAV, both the recommended and final programmed values.
- Pacing Chamber (BiV or LV Only), both the recommended and final programmed values.
- Rationale if the SmartDelay recommendations are not followed

The following documents from the SmartDelay test are required:

- Set EGM channels to RA, RV, and LV. Obtain ECG/EGM strips at the paper speed of 100 mm/s for approximately 3-5 representative beats during the Atrial Sense test and Atrial Pace test, respectively. The following values are required to be measured from the ECG/EGM strips:
 - Asense-RVsense, Asense-LVsense, Apace-RVsense, and Apace-LVsense intervals for each of the representative beats
 - Calculate the mean value for each of the 4 intervals from these representative beats

Record the Subject ID and visit information (Enrollment, 6 Month, or 12 Month) on each ECG/EGM strip. Copies of all ECG/EGM strip should be submitted to BSC quarterly or more frequently, and before study ends. The data collected in this test will be used for future product feature enhancement or development, and are not associated with the primary and ancillary objectives. A deviation is not required if the ECG/EGM strips are not sent to BSC.

- Print a copy of the Settings Changes Report from the PRM immediately after running the SmartDelay test and before any other setting changes are made and programmed. This report will display the recommended changes to the SAV, PAV, and Pacing Chamber at pending status.

If the SmartDelay test fails to complete, re-perform the test to obtain the recommended value. If the SmartDelay test was complete but not successful, the recommended value will be the nominal value used by SmartDelay. The SmartDelay test should be limited to two attempts in total.

11.6.10. LV VectorGuide Test

Non-Responder Group with No LV MSP

For Non-Responder Group subjects who did not receive the LV MSP therapy, it is required that the RV-LV interval value be measured from all 4 electrodes as cathode (LVTip1,

LVRing2, LVRing3, and LVRing4) by starting the LV VectorGuide test; however, it is not required to complete all steps of the LV VectorGuide test once the RV-LV intervals are collected. If the LV VectorGuide test is completed, also provide the number of viable pacing vectors.

Subjects must have RV and LV sensed beats for the test to be successful. If the subject does not tolerate a low intrinsic heart rate, stop the test and provide the rationale for not completing the required test (e.g. subject needs RV pacing support).

The following values are required to be collected in the Non-Responder Group:

- Select the unipolar vectors and run the RV-LV Delay test for all 4 unipolar vectors to obtain RV-LV delay values.

The following values are required to be collected only if the LV VectorGuide test is completed:

- Number of viable pacing vectors (See definition in **Section 8.2**)

The following document is required in the Non-Responder Group:

- Print a copy of the LV VectorGuide Report from the PRM.

Non-Responder Group with LV MSP on

For subjects with the LV MSP turned on, it is required to use the LV VectorGuide test to assess viable LV pacing vectors from all 17 pacing vectors.

For all 17 pacing vectors, the following values are required to be collected for subjects in the Non-Responder Group:

- RV-LV delay
- LV pacing impedance
- PNS test results
- LV Quick Capture threshold test
- Number of viable pacing vectors (See definition in **Section 8.2**)

The following document is required for subjects with the LV MSP on:

- Print a copy of the LV VectorGuide Report from the PRM.

